either the center of the screen or the periphery. The child will also view different shapes and faces (happy, sad, angry, scared, and neutral) while engaged in the computer game. Following the game, the child will answer questionnaires (general questionnaire, SCARED, Childhood Depression Inventory (CDI), MFQ, and Pubertal Development Scale(PDS)) and participate in the child version of the K-SADS and PARS.

F3 Visit 2

Neuroimaging Visit:

MRI Simulation/Stillness Training: Child participants will complete a MRI training session to collect data on movement inhibition and prepare subjects for future MRI testing. Research indicates that an MRI simulation exercise prior to scanning increases the likelihood of a successful scan. Given that, an introduction to/explanation of the scanning procedure and a simulation exercise will be introduced at the conclusion of the child assessment. The child interviewer will engage the child in an MRI simulation. In this simulation, the child will practice lying still in a mock scanner environment. The child will practice lying still while listening to recorded MRI sounds and receiving visual feedback of their head movement. Feedback will be provided using motion tracking software, MoTrak 3D, connected to a video screen viewed from the scanner by the research subject. Subject movement and responsiveness to the training procedures will be recorded. Children will also be shown a video in which the scanning center is introduced and the scanning procedure is explained to the child. In the video, the child will see another child participating in the MRI procedure.

The NEUROIMAGING TRAINING could take place on the same day following the IN-PERSON ASSESSMENT, on the same day before the NEUROIMAGING VISIT, or on its own day, depending on the preference of the participant.

Before the MRI scan, parents will complete the MRI Safety checklist to ensure the child safety in the scanner and the child will complete a shortened version. The child will complete a 90 minute MRI scan before and after the cognitive training. We acquire a T1-weighted MP-RAGE, a T2 image, 4 five-minute "resting" functional scans, and 4 four-minute "task" functional scans. During the resting scans, the subjects with fixate a cross and during task blocks, subjects will complete the attention tasks. There will be no contrast used for this MRI scan.

F4 Visit 3-10

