The child will participate in 8 thirty minute training sessions, twice a week for four weeks. They will complete the cognitive training program that has been designed by [name].

On the day of sessions 2, 4, 6, and 8 subjects and parents complete the SCARED either in office or by a secure e-mail survey invitation via REDcap in order to assess anxiety over treatment. After session 8, subjects will be asked to rate tolerability of the training on a 5 point Likert scale.

F5 Visit 11

This visit will be after all 8 training sessions are completed and is identical to visit 1.

F6 Visit 12

This visit will be after all 8 training sessions and visit 11 are completed and is identical to visit 2.

Follow-up via Phone/Zoom

A member of the research team will explain that this is completely optional and will review the online survey process with the family over the phone or zoom. If the family agrees to participate, the research team member will e-mail a RedCap survey link that will start with the consent form. Researcher will walk participant through how to complete the surveys over the phone or zoom. Participants will have adequate time to review the consent document and there will be an e-mail address provided if the participant should have any questions. The participants e-signature through REdCap will have a time stamp. After the consent is signed, research staff will send an electronic copy of the signed consent document to the participant via e-mail.

G Statistical Plan

G1 Sample Size Determination and Power

Power analyses for two-tailed, two independent groups (active versus sham) comparisons were performed using G*Power 3.1. Based on prior work, we expect training to have a minimum effect size of 0.3 for changing symptoms of anxiety. Based on this effect size, we have 83% power to detect group differences in treatment effects (n=90, plus 10% failure). Power calculations are not computed for fMRI analyses because we have no effect size estimate; sample size is similar to other recent pilot studies.

G2 Interim Monitoring and Early Stopping

Subjects may withdraw from the study at any time. Each cognitive training session takes place in the lab. Study staff will converse with study subjects before and after each training session in order to assess for any adverse events.

G3 Analysis Plan / Statistical Methods

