The primary outcome will be reduction in symptoms of anxiety as measured by the SCARED in study Phase 2. Total SCARED scores at sessions 2, 4, 6, and 8 will be subtracted from the baseline SCARED score, yielding a delta SCARED score for each

visit. These data will be analyzed with a mixed random effects repeated-measures model. In this model, time, treatment (active versus sham), and time x treatment interaction are fixed effects; baseline SCARED scores and subject within treatment are random effects; and delta SCARED scores are the dependent variable. Our hypothesis predicts a significant time x treatment interaction, with a greater decrease in anxiety from pre- to post- training in the active relative to the sham group. Secondary outcomes will include symptoms of anxiety on the PARS and diagnostic status.

We will test whether active versus sham training significantly reduces symptoms in children with anxiety disorders. The primary outcome will be reduction in symptoms of anxiety as measured by the PARS. We will perform a 2 x 2 ANOVA with treatment arm (active versus sham) and time (pre- versus post-training) as effects of interest.

G4 Missing Outcome Data

We will use an intention-to-treat analysis and carry the last observation forward. Because this is a pilot study, we will also compare active versus sham treatment among completers in a follow-up analysis.

G5 Unblinding Procedures

The principal investigator will be made aware of each subject's assignment after that subject has completed all study procedures including post-treatment psychiatric assessment.

H Data Handling and Record Keeping

H1 Confidentiality and Security

Telephone conversations about the study, the consent process, and all portions of the study will take place in a private office. All subjects will be marked with a random identification number so names will not be recorded on any of the data. All data will be stored in locked filing cabinets and on password protected computers. Also, only the research team will have access to study information. Participants can refuse to answer any questions and withdraw from the study at any time.

H2 Training

All current study staff have extensive experience in study procedures, based on similar prior studies performed in the lab. Any new personnel will be trained by current study staff.

H3 Case Report Forms and Source Documents

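### Children who stop training early have no scheduled post-training PARS, so the intention-to-treat PARS analysis rests on completers' data plus carried-forward baselines

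*Combined protocol and SAP*

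**What the plan says.** The PARS is taken at Visit 1 (F2), where parents are interviewed and children "participate in the child version of the K-SADS and PARS". The next PARS is at Visit 11, for which F5 says: "This visit will be after all 8 training sessions are completed and is identical to visit 1". F6 ties the second scan to the same event: "This visit will be after all 8 training sessions and visit 11 are completed and is identical to visit 2". No PARS, K-SADS or scan is planned in between. The SCARED is taken more often. F4 says "On the day of sessions 2, 4, 6, and 8 subjects and parents complete the SCARED", either in the office or through an e-mailed REDCap survey.

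On leaving, 2.f, 2.g and G2 say that participation is voluntary and may end at any time. None of them describes an assessment for a child who gives up training but would still attend. E1 says in general terms that subjects have follow-up assessments. The optional phone or Zoom follow-up consists of surveys and does not name the PARS.

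G3 names two primary outcomes. The first is the SCARED: "The primary outcome will be reduction in symptoms of anxiety as measured by the SCARED in study Phase 2", analysed with a repeated-measures mixed model. The second is the PARS: "The primary outcome will be reduction in symptoms of anxiety as measured by the PARS", analysed by arm and by time (before and after training). On missing data G4 says "We will use an intention-to-treat analysis and carry the last observation forward", and adds that "we will also compare active versus sham treatment among completers in a follow-up analysis".

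**The concern.** An intention-to-treat comparison needs outcomes from children as randomised, whether or not they finish. When the outcome visit is defined by finishing training, stopping training and losing the outcome become the same event. Part of the missing data then comes from the schedule and not from families declining, and that part is avoidable: some children who stop might have attended if asked.

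Carrying the baseline forward does not recover the lost information. It assigns these children no change. If the arms lose children at different rates, the comparison reflects that difference as well as any treatment effect. Only the active task contains distractor boxes, so unequal stopping is conceivable, but the documents give no data on it. The same gap affects diagnostic status (a secondary outcome in G3), the fMRI (the secondary aim) and the tolerability rating, which F4 asks for only after session 8.

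**Working it through.** **1. Observed data by point of stopping** (from F2, F4 and F5, followed as written)

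| Last session completed | PARS values | SCARED scores from training sessions |
|---|---|---|
| 0 or 1 | baseline only | 0 |
| 2 or 3 | baseline only | 1 |
| 4 or 5 | baseline only | 2 |
| 6 or 7 | baseline only | 3 |
| 8 | baseline and Visit 11 | 4 |

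**2. Effect of G4 on the PARS.** For a child who stops, the last observation is the baseline. The imputed change is baseline minus baseline = 0, whatever actually happened to the child.

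**3. Intention-to-treat against completers.** Both PARS analyses use the same observed Visit 11 values. They differ only in the zeros added for children who stopped.

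**4. The plan's own figures.** G1 states 83% power for an effect size of 0.3, with n=90 plus 10% failure. Alpha and the effect-size metric are not given. At two-sided 0.05 (assumed) with 45 per arm, 0.3 read as Cohen's d gives 29%. Read as Cohen's f (d = 0.6) it gives 80%, or 84% with 99 or 100 children. Read as a correlation it gives 82% to 84% at N=90. The figure is therefore ambiguous, and nothing in this point depends on it. The 10% failure is not defined as stopping training either. If it were 10% of 90, it would be 9 children; it may instead be an allowance on top of 90.

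**5. Equal stopping (illustration).** Let q be the fraction that stops in each arm, D the difference in mean change among completers, m an arm's completer mean change, and 1 the SD of change.

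- Arm mean after imputation = (1 − q) × m + q × 0.
- Difference between arms = (1 − q) × D. With q = 0.10 this is 0.90 × D: 0.27 for D = 0.3, or 0.54 for D = 0.6.
- Arm variance = (1 − q) + q(1 − q)m².
- With sham improvement from 0 to 1 SD and 45 per arm, power falls from 29% to 24–27% for D = 0.3, and from 80% to 69–75% for D = 0.6. An analysis of 81 completers alone would have 27% and 76%.

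Whether the factor 0.90 is too small, too large or right depends on how the children who stopped actually fared, and that is the information not collected.

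**6. Unequal stopping with no true effect (illustration).** Suppose all children in both arms improve by μ, and fractions q_A (active) and q_S (sham) stop.

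- Apparent active-minus-sham difference = μ × [(1 − q_A) − (1 − q_S)] = μ × (q_S − q_A).
- q_A = 0.05, q_S = 0.15, μ = 0.5: 0.5 × 0.10 = 0.05 SD.
- Same fractions, μ = 1.0: 1.0 × 0.10 = 0.10 SD.
- With the fractions swapped, the sign reverses.

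Against G1's 0.3 read as d, this is 0.05/0.3 = 17% to 0.10/0.3 = 33%. Read as f (d = 0.6), it is 0.05/0.6 = 8% to 0.10/0.6 = 17%.

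The values of q, μ, D and the SD in steps 5 and 6 are assumptions; only the 10%, the 90 and the 0.3 stand in the plan.

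**The case against.** The strongest reply is that F5 merely orders the expected visits. It does not exclude a child who stopped, and E1 mentions follow-up assessments without condition. That stands: a reader might infer that the protocol forbids a post-training visit for these children, but the text is silent on them. The silence still matters. F5 and F6 are the only scheduling text, staff following them have no trigger to book the visit, and two sites could resolve the gap differently.

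A reader might also infer that the intention-to-treat analysis holds no outcome data at all beyond completers. For the SCARED, which G3 also names as primary, that is wrong. A child who quits after five sessions has scores from sessions 2 and 4 in the model. What is missing is the SCARED after stopping.

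Third, the completer analysis is not empty as a check. Comparing it with the intention-to-treat result shows how far the PARS answer depends on the inserted zeros. It cannot show how children who stopped actually fared.

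Fourth, the quantified harm comes from the carry-forward rule as well as from the schedule, and every stopping rate and improvement used is assumed. That also stands. Boredom and fatigue are listed as risks of the training in general, not of one arm, and similar stopping in both arms would produce no spurious difference in the setting of step 6.

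Finally, one might want every visit and every SCARED moved to calendar time. For children still in training that would change what is measured: G3 frames the PARS comparison as before and after training, and F4 collects the SCARED to follow anxiety over the course. The gap concerning children who stop does not require it.

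**Conclusion.** The point holds for the PARS, the K-SADS and the fMRI. As written, the plan schedules no post-training assessment for a child who stops early, so the intention-to-treat PARS analysis is completers' observed data plus changes of 0. The SCARED loses only what would have followed stopping. This is more than a missing detail, because G4 promises an intention-to-treat answer that the visit schedule does not supply with data.

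The size of any bias is unknown. The 0.05 to 0.10 SD figure rests on 5% versus 15% stopping, a shared improvement of 0.5 to 1.0 SD and no true effect, none of which comes from the documents. They do not support saying that the arms will differ in stopping, or that a given number of the 90 children will be affected. The change is worth making because the loss is avoidable and the remedy uses visits already planned.

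**What to change.** - **F5 and F6:** state that Visits 11 and 12 are offered to every randomised child. For a child who stops training early, schedule them at the time the 4-week course would have ended, within a stated window.
- **2.f and 2.g:** state that stopping training is not withdrawal from assessment, and record the two separately.
- **F4:** keep sending a child who has stopped the remaining SCARED surveys through the existing REDCap link.
- **G4:** say that observed post-training values from children who stopped enter the intention-to-treat analysis, so that carry-forward applies only where no assessment was obtained.

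The cost is a wording amendment, plus visit payments and staff time for the children who stop early and agree to attend. The protocol gives payment rates but no budget, so whether this money is already set aside cannot be read from it.

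The protocol version is dated 12/10/2020, after the planned period of January 2018 to June 2019. If data collection has ended, report by arm how many children stopped training, how many had Visit 11, and when it took place.

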There are minimal risks associated with this study. Parents and children may feel uncomfortable or bored during the first assessment during the clinical interview. There is also a risk of breach or confidentiality. During the cognitive training, risks for child participants include boredom and very slight physical discomfort due to sitting and using a chin rest. MRI scans involve no major risks for subjects without implanted metal objects. Subjects are extensively screened before scanning and are not allowed to participate if they have any implanted metal objects. Additional minor potential risks of MRI are discomfort from being in a small space and lying still in one position for a long time. There are also loud noises made by the scanner but subjects will wear earphones to mask the sound.

The benefits to this study are that the treatment could potentially alleviate symptoms and distress in a participant. Also the participant is receiving a free diagnostic assessment, which typically is expensive and takes a long period of time to get an appointment.

2.f Early Withdrawal of Subjects

Subject participation in the study is completely voluntary and they can choose to withdraw at any time.

2.g When and How to Withdraw Subjects

If subjects meet exclusion criteria in their initial in office assessment, they will be withdrawn from the study. Subjects may also choose to withdraw from the study at anytime.

E3 Study Device

Cognitive Behavioral Training

3.a Description

The cognitive training program is designed by [name]. It is designed to lower activity in the VAN by reducing the influence of extraneous, salient stimuli, thereby reducing stimulus-driven attention and potentially anxiety.

To begin a trial, subjects fixate a central crosshair; 150 ms later, an arrow "cue" appears at the center of the screen and subjects are instructed to voluntarily direct their attention toward the location indicated by arrow. Following a random delay of 1, 2, or 3 seconds, subjects indicate whether a "target" (that always appears at the location indicated by the initial arrow cue).

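### G1's 83% power for an effect size of 0.3 names no metric or alpha: read as Cohen's d, 90 children give about 29%, and 83% is approached only if 0.3 is f or r (d about 0.60 to 0.63)

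*Combined protocol and SAP*

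**What the plan says.** G1 (Sample Size Determination and Power) describes the calculation in three sentences. The test: "Power analyses for two-tailed, two independent groups (active versus sham) comparisons were performed using G*Power 3.1". The effect: "we expect training to have a minimum effect size of 0.3 for changing symptoms of anxiety", attributed to prior work with no figure. The result: "Based on this effect size, we have 83% power to detect group differences in treatment effects (n=90, plus 10% failure"). G1 gives no effect-size metric, alpha, standard deviation, endpoint or correlation between repeated measurements.

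Ninety is the total, not the number per arm. A1 enrols 90 across two sites, I4 sets 90 as the number to randomise (2.5 per month x 2 sites x 18 months = 90), and 3.c allocates 50/50, so there are 45 per arm.

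G3 plans different analyses. For the SCARED: "These data will be analyzed with a mixed random effects repeated-measures model", and "Our hypothesis predicts a significant time x treatment interaction". For the PARS: "We will perform a 2 x 2 ANOVA with treatment arm (active versus sham) and time (pre- versus post-training) as effects of interest". G1 ties its power to neither.

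Two other passages bear on the 10% failure allowance. G4: "We will use an intention-to-treat analysis and carry the last observation forward". Section 2.g: "If subjects meet exclusion criteria in their initial in office assessment, they will be withdrawn from the study".

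**The concern.** For a two-group comparison of means, an effect size of 0.3 is normally read as Cohen's d, and 45 per arm is far too few to give 83% power for that. If d was meant, the comparison would miss a true effect of that size about 7 times in 10, while G1 implies about 1 in 6. If another metric was meant, the minimum effect is about twice what the text suggests on its usual reading, and it needs a justification that the documents do not give. Either way, someone relying on G1 could take a null result as evidence against a modest benefit when the trial could not show that.

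The 10% failure allowance adds a second uncertainty, because G1 does not say whether 90 is the number before or after it.

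**Working it through.** **Inputs.** From the documents: two-tailed, two independent groups, effect size 0.3, stated power 83%, n = 90 (G1); 1:1 allocation (3.c). Assumed, because it is not stated: two-sided alpha 0.05.

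**Method.** Two-sample t test, power from the noncentral t distribution with N - 2 degrees of freedom and noncentrality d x sqrt(N/4).

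**1. Trying to reproduce 83% with 0.3 as d.** At N = 90 the noncentrality is 0.3 x sqrt(22.5) = 1.42, against a critical value of 1.987.

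| Analysed N | Power at d = 0.3 |
|---|---|
| 81 (90 x 0.9) | 26.6% |
| 90 | 29.1% |
| 99 (90 x 1.1) | 31.5% |
| 180 (90 per arm) | 51.7% |

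The figure is not reproduced. At N = 90 a one-sided alpha of 0.05 gives 40.8%, and a one-sided alpha of 0.10 gives 55.4%. Reaching 80% takes 176 per arm, and 83% takes 190 per arm.

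**2. 0.3 as Cohen's f.** For two equal groups d = 2f = 0.60. Power is 76.0% at 81, 80.4% at 90, 83.3% at 97 and 84.0% at 99.

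**3. 0.3 as a correlation r.** d = 2r/sqrt(1 - r^2) = 0.6/sqrt(0.91) = 0.629, and the two-group test has 83.9% power at 90. As a test of a correlation, the Fisher z approximation gives 82.3% and the exact bivariate normal calculation 82.7%. The last rounds to 83%, but it is not the two-group test that G1 names.

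**4. What 90 children can detect.** 80% power corresponds to d = 0.60 at 90 analysed and 0.63 at 81. 83% power at 90 corresponds to d = 0.62. The 95% confidence interval half-width for the unadjusted difference at 90 is 1.987 x sqrt(2/45) = 0.42 SD.

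**5. Could G3's analyses supply the 83%?** Assumed here: a true effect of 0.3 raw-score SD, N = 90, and equal correlation rho between any two measurements.

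| Test | Standardised effect | rho 0.3 | rho 0.5 | rho 0.7 | rho needed for 83% |
|---|---|---|---|---|---|
| Pre-post change (2 x 2 interaction) | 0.3/sqrt(2(1 - rho)) | 22% | 29% | 44% | 0.88 |
| Baseline-adjusted mean of four visits, constant effect | 0.3/sqrt((1 + 3rho)/4 - rho^2) | not run | 63% | 75% | 0.77 |
| Linear time x treatment trend, effect growing evenly to 0.3 SD at session 8 | 0.75/sqrt(20(1 - rho)) | 16% | 20% | 30% | 0.93 |

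In the last row the effects are 0.075, 0.15, 0.225 and 0.30 at sessions 2, 4, 6 and 8, and the contrast is (-3, -1, 1, 3). If the effect were instead constant over sessions 2 to 8, that interaction would have only about 5% power, because there would be no divergence left to detect.

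**6. Support for d of about 0.6.** G1 cites prior work without a number. D2 reports no clinical data on this program and says related programs work, without giving a size. B1 describes the effect of attention bias modification on symptoms as at most modest. It hopes that this program will do better, but gives no figure.

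**7. The 10% failure allowance.** Three readings are open: 10% non-completion (90 x 0.9 = 81 completers); 10% excluded at the in-office assessment under 2.g (99 to 100 assessed, 90 randomised); or 10% added to 90 randomised (99 to 100), which would not match I4.

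**The case against.** The strongest reply is that no error has been shown. If the sponsor used r, 83% is recovered at 90, and if f, it is bracketed by 90 and 99, a range that the 10% allowance could cover. That stands, and the point is therefore not put as a proven slip. What remains is that G1 does not say so, and on either reading the minimum effect is about 0.6 SD without support.

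A second reply is that the planned repeated-measures analyses are more powerful than a two-group t test, and that other G*Power settings also land near 83%. One is the within-between interaction with f = 0.15 and correlation 0.5, which gives 80.4% at 90 and 84.0% at 99. But in that setting f = 0.15 means a between-arm difference in change of 0.6 SD; a 0.3 SD difference is f = 0.075 and returns 29%. For a 0.3 SD raw effect, G3-type analyses need correlations of about 0.77 to 0.93, and G1 states none. The figures in step 5 rest on assumptions that are not in the documents, and the baseline-adjusted mean is not a test that G3 specifies. They show only that the planned repeated measures do not rescue the claim by default.

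A third reply is that this is a pilot and that the remedy is wording. That is fair as to cost. But C1 makes efficacy the primary aim, and G1 chose to claim a specific power.

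Finally, the allowance does not drive the result: d = 0.3 gives 27 to 32% on every reading of it.

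**Conclusion.** The concern holds. For the test that G1 names, 0.3 read as d gives about 29% power with 90 children (27% at 81, 32% at 99), not 83%. On that test 83% is approached only when 0.3 is f or r, that is, d of about 0.60 to 0.63. The documents do not show which metric was used, so the finding is that the stated power cannot be verified and is unreachable on the natural reading. With a half-width of about 0.42 SD, even an observed difference of zero on the unadjusted comparison would not exclude d = 0.3.

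This rests on an assumed two-sided alpha of 0.05 and equal arms. The two-group figures need no other assumption.

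**What to change.** Keep 90 randomised and restate G1:

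- Name the effect-size metric, alpha, the G*Power procedure and the analysed N.
- State that, for an unadjusted two-group comparison at two-sided alpha 0.05 with 90 analysed, power is 80% for a standardised mean difference of about 0.60 and about 29% for 0.3 (with 81 analysed, 0.63 and 27%).
- If f or r was intended, say so, give the equivalent d (about 0.60 or 0.63) and justify it as the minimum effect.
- If power is claimed for a G3 analysis, state which test (average effect, pre-post change or time x treatment interaction), the assumed correlation and the number of measurements.
- Define the 10% failure allowance and say whether 90 is before or after it, so that G1 agrees with A1, I4 and G4.
- Commit to reporting the effect with its 95% confidence interval, and note that a null result on the unadjusted comparison would not rule out d = 0.3.

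The cost is wording in G1, with no extra children. The stated power becomes less favourable, or a larger minimum effect has to be defended. By I4's timetable (January 2018 to June 2019), the change affects how results are read, not recruitment.

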[A novel mechanism-based treatment for pediatric anxiety disorders]

Principal Investigator:

[name]., Ph.D.

Version Date/Number:

2 - 12/10/2020

A Introduction

A1 Study Abstract

Anxiety disorders are the most common form of pediatric psychiatric illness, affecting up to 30% of youth by age 18.¹ These disorders often produce marked impairment,² are associated with aberrant neurodevelopment,³ and predict high risk for various forms of adult psychopathology.⁴ While successful early intervention can occasionally interrupt this cascade,^{5,6} most affected children remain symptomatic even with the best available treatments.⁷ This study tests a novel, safe, mechanism-based treatment for pediatric anxiety disorders: a computer-delivered cognitive training program designed to rehabilitate the brain's ventral attention network (VAN). 90 children between the ages of 7 and 17 years of age will be enrolled at 2 sites (45 at Washington University and 45 at the NIMH). Children will be randomly assigned to active versus placebo cognitive training. Clinical symptoms and brain activity (measured with functional magnetic resonance imaging: fMRI) will be measured before and after training. This study has the potential to provide a novel, safe treatment for anxiety disorders as well as uncover the neural associates of this treatment.

A2 Primary Hypothesis

The active cognitive training program decreases symptoms of anxiety in children with anxiety disorders relative to sham training.

A3 Purpose of the Study Protocol

This study protocol is to be used as the working document for the study team to ensure that the conduct of the research is consistent with what has been approved by the IRB.

B Background

B1 Prior Literature and Studies

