All data will be labeled with a number and not the participant's name. All electronic data will be stored in a locked cabinet and on password protected and encrypted data storage devices/computers. Paper/hard copy records will be stored in a locked filing cabinet in a

locked room.

H4 Records Retention

All data will be retained and destroyed once the study is completed.

Study Administration

I1 Organization and Participating Centers

National Institutes of Mental Health, Bethesda, Maryland & Washington University School of Medicine, St. Louis, MO

12 Funding Source and Conflicts of Interest

Institutional Grant/Award: FBJH/ICTS

Federal Agency: NIH, National Institute of Health

ATTENTION AND RELATED FUNCTIONAL BRAIN NETWORKS IN PEDIATRIC

ANXIETY DISORDERS

There are no conflicts of interest.

13 Subject Stipends or Payments

Caregivers and child will be paid a total of \$25 an hour together for each in person assessment, \$50 for the completion of the cognitive training, and an additional \$25 per hour for neuroimaging sessions.

Caregivers and child will be paid a total of \$50 for completion of the follow-up surveys on a Forte Card.

14 Study Timetable

Our goal is to randomize 90 subjects to active versus sham treatment over 18 months at two sites (Washington University and the National Institute of Mental Health). To achieve, this goal we will recruit, on average, 2.5 subjects per month per site. The current plan is to perform this study from January 2018 through June 2019.

J Publication Plan

Manuscripts reporting the primary outcome of the study as well as the neural effects of training will be written at the completion of the study.

K Attachments

K1 Informed consent documents

Novel Treatment Study Assent

Novel Treatment Study Imaging Assent

Novel Treatment Study Imaging Consent

Novel Treatment Study Informed Consent

Novel Treatment Consent for Phone Screen

K2 Questionnaires or surveys

Screen for Anxiety Related Disorders (SCARED)

Mood and Feelings Questionnaires (MFQ)

Kiddie Schedule for Affective Disorders and Schizophrenia Present and Lifetime Version(K-SADS-PL)

Childhood Depression Inventory (CDI)

Attention General Questionnaire

Contact Information Sheet

Pediatric Anxiety Rating Scale (PARS)

Pubertal Development Scale (PDS)

Family Interview for Genetic Studies (FIGS)

Conners

L References

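### G1 ties its 83% power to 90 children plus a 10% failure allowance, but every recruitment figure stops at 90 and the allowance is never provided for

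*Combined protocol and SAP*

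**What the plan says.** G1 describes the calculation this way: "Power analyses for two-tailed, two independent groups (active versus sham) comparisons were performed using G*Power 3.1". The effect size is given as "we expect training to have a minimum effect size of 0.3 for changing symptoms of anxiety", and the result as "we have 83% power to detect group differences in treatment effects (n=90, plus 10% failure". G1 names no effect-size metric and no alpha, and does not say what counts as a failure.

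The abstract (A1) states that "90 children between the ages of 7 and 17 years of age will be enrolled at 2 sites", split 45 and 45. The Study Timetable says "Our goal is to randomize 90 subjects to active versus sham treatment over 18 months at two sites" and that "we will recruit, on average, 2.5 subjects per month per site". Section 2.g adds: "If subjects meet exclusion criteria in their initial in office assessment, they will be withdrawn from the study".

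G4 plans an intention-to-treat analysis with last observation carried forward, and a follow-up comparison among completers. G3 plans an arm-by-time ANOVA for the PARS, measured before and after training, and a repeated-measures model for the SCARED, collected at sessions 2, 4, 6 and 8. It calls each of them the primary outcome.

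**The concern.** Read naturally, G1 means 90 analysable children plus about 10% more, that is 99 or 100. A1 and the timetable contain no such surplus. If the 10% failures occur after randomisation, the 83% belongs to a sample the plan does not recruit, and a null result would be judged against power the trial did not have.

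There is also a mismatch in the counts. A1 counts 90 as enrolled and the timetable counts 90 as randomised. Consent is signed on the day of the in-person assessment (2.c), and 2.g withdraws children found ineligible there. If any such child counts as enrolled, the two totals cannot both be 90.

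**Working it through.** **Recruitment.** 2.5 per month × 2 sites × 18 months = 90, with no surplus. Keeping 90 evaluable after 10% loss needs 90 / 0.9 = 100 randomised (or 90 × 1.1 = 99 if the 10% is simply added). Losing 10% of 90 leaves 90 × 0.9 = 81; that figure is derived here and does not stand in the plan.

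**Inputs.** Two-tailed, two independent groups, effect size 0.3 (G1); 1:1 allocation (2.d). Alpha 0.05 is assumed.

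**Formula.** Power = P(|T| > t at 0.975 with N − 2 df), where T is noncentral t with noncentrality d√N / 2. The value 0.3 is taken three ways:
- as d: d = 0.30;
- as f: d = 2f = 0.60;
- as r: d = 2r / √(1 − r²) = 0.6 / √0.91 = 0.629. As a check, Fisher z: Φ(0.3095 × √(N − 3) − 1.96).

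**Results, starting with the plan's own N = 90.**

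| Analysed | 0.3 as d | 0.3 as f | 0.3 as r (t / Fisher z) |
|---|---|---|---|
| 90 | 29.1% | 80.4% | 83.9% / 82.3% |
| 81 | 26.6% | 76.0% | 79.8% / 78.0% |
| 99 | 31.5% | 84.0% | 87.2% / 85.8% |
| 100 | 31.8% | 84.4% | 87.6% / 86.2% |

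For example, with f at N = 81 the noncentrality is 0.60 × 9 / 2 = 2.70, giving 76.0%. The stated 83% is matched to within about a point by r at 90 or f at 99. No metric matches it at 81, and d does not come near it at any of these sizes.

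**All 90 kept, failures carried forward.** Work in units of the completers' SD of change. Sham improves by c and active by c + d. In each arm 10% record only a fraction k of their change.
- Mean difference = d(0.9 + 0.1k).
- Variance in an arm with mean change μ = (0.9 + 0.1k²)(1 + μ²) − (0.9 + 0.1k)²μ².

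Zero change (k = 0, baseline carried forward) at d = 0.60:
- c = 0: difference 0.54; variances 0.900 and 0.932; effective d = 0.54 / 0.957 = 0.564; power 75.4%.
- c = 1: difference 0.54; variances 0.990 and 1.130; effective d = 0.54 / 1.030 = 0.524; power 69.2%.

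Over c from 0 to 1 SD:

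| Change kept by failures | 0.3 as f | 0.3 as r |
|---|---|---|
| none (k = 0) | 69-75% | 73-79% |
| half (k = 0.5) | 78-79% | 81-83% |
| three-quarters (k = 0.75) | 80% | 83-84% |

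With 0.3 as d and zero change, power is 24-27%. The values of k and c are assumptions; the plan gives neither.

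**The case against.** The strongest reply is G4. Dropouts stay in the main analysis, so it holds up to 90 children, and 81 describes only the completer follow-up. This stands. A reader might infer from G1 that just 81 children will be available for the main analysis, and the documents do not say that. It does not rescue the 83% for the PARS, which has one pre and one post measurement: a missing post score carries baseline forward. It may rescue the figure for the SCARED if 0.3 is r, because interim scores carry partial change.

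A reader might also infer that 83% is out of reach under any calculation at 81. That goes too far. A G*Power-type within-between test with two time points, closer to the arm-by-time ANOVA in G3, has noncentrality f² × N × 2 / (1 − ρ), where ρ is the pre-post correlation. At N = 81, f = 0.15 gives 76.0% at ρ = 0.5, 83% at ρ of about 0.58 and 84.7% at ρ = 0.6; f = 0.3 gives over 96% even at ρ = 0. But G1 describes a comparison of two independent groups and states no correlation, so this is not the calculation it reports.

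Third, failure could mean exclusion before randomisation. Then 90 randomised agrees with n = 90, the allowance sits upstream, and A1 and the recruitment rate are what need rewording. The text does not exclude this. On that reading the 83% makes no allowance for loss after randomisation.

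Finally, the unnamed metric matters more: at 90 analysed it moves power between 29% and 84%, against 2 to 5 points for going from 90 to 81. That is correct, and power cannot be restated until the metric is named. Naming it would still not settle whether the target is 90 or 100.

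**Conclusion.** The inconsistency is real: the 10% allowance in G1 is in none of the enrolment, randomisation or recruitment figures. For the test G1 names, at two-sided alpha 0.05 (assumed), 81 completers give about 27% (d), 76% (f) or 78-80% (r), all short of 83%. With all 90 kept and 10% at zero change, power is about 69-75% (f) or 73-79% (r). With half to three-quarters of the change carried forward it is about 81-84% for r, so the stated figure can roughly survive on that one reading.

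The documents do not support saying that the main analysis shrinks to 81, or that no calculation reaches 83%. The conclusion is limited to the two-group test in G1, and the shortfall depends on failure meaning loss after randomisation.

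**What to change.** In G1:
- name the effect-size metric and the alpha;
- say whether failure means loss before or after randomisation;
- state 90 randomised;
- restate the power for the named metric, once for the intention-to-treat analysis with 10% failures carried forward and once for 81 completers.

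Alternatively, state that 83% at 90 evaluable corresponds to 90 / 0.9 = 100 randomised and that this is not planned. This route too requires the metric to be named: at 90 evaluable, r gives 82-84%, f gives 80% and d gives 29%.

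In A1, change enrolled to randomised, so that the count matches the timetable and in-office exclusions do not come out of the 90.

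The cost is wording and a less favourable stated power; restating needs no extra children. If 0.3 is f or r, the figure falls by about 3 to 7 points at 81 completers (83 − 79.8 = 3.2; 83 − 76.0 = 7.0) and by up to about 14 under zero-change carry-forward (83 − 69.2 = 13.8). If 0.3 is d, it falls by more than 50 points (83 − 29.1 = 53.9 even with all 90 and no dilution).
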